## **METHODS**

**Study design:** We propose to conduct a pilot non-randomized-controlled trial to evaluate the impact of “Tomando control de su salud”, an evidenced-based intervention for chronic disease self-management, in the quality of life of patients living with Long-COVID in Puerto Rico.

**Participant selection:** We will invite patients from our cohort study during the 12-month follow-up call. All participants identified with conditions associated with Long COVID or chronic diseases will be invited to participate. These are the inclusion and exclusion criteria:

Inclusion criteria:

- 1) Adult patients 21 years or older
- 2) Participant of PR-COAS cohort that completed the last interview (12-month-follow-up) and authorized to be contacted for further studies.
- 3) Having at least one chronic condition (excluding cancer) diagnosed by a physician or healthcare provider.
- 4) Ability to attend weekly sessions (applicable to intervention group).

Exclusion criteria

- 1) Any clinical or cognitive impairment that limits the participant's ability to decide to participate in the study or complete the interviews.
- 2) Presence of a life threatening or extreme medical condition.

- 3) Planning to move out of the municipality within the next year.

**Sample size determination:** The primary goal of this study is to pilot the potential implementation of this intervention for Long COVID patients. We are therefore not powering for a definitive assessment of the difference between any two groups. However, we expect the preliminary data from this study to provide adequate pilot data from which we will be able to determine the required sample size for a larger scale study. The sample selected will provide an estimate of the effect size and thereby allow preliminary evaluation of the clinical utility associated with the intervention.

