**Sampling strategy:** Participants with Long-COVID and chronic diseases that agree to participate in the intervention will be allocated into one of the study intervention groups that will participate in the “Tomando Control de su Salud” workshops. Those not interested in participating in the intervention will receive general information about chronic disease management available at the CDC website in Spanish, by email, regular postal mail or in person, in addition to their regular health care and will be asked to answer the post questionnaires approximately 3 months after the last interview of the PR-COAS cohort. With an estimated participation rate of about 25 – 30% we expect to identify between 20-25 participants with Long-COVID with at least one-chronic condition. We estimate that about half will be interested in receiving the intervention; therefore, we expect to have about 20-25 participants in the intervention arm divided into two or three workshops of 8 – 12 participants based on the number of patients recruited and about 30-40 participants in the general care group. Figure 2 summarizes the expected recruitment and procedures.

**Proposed intervention:** “Tomando control de su salud” (Spanish Chronic Disease Self-Management)  is a culturally appropriate program developed in Spanish to support Hispanics

patients to build confidence in their ability to manage their health. This intervention was developed by Lorig et al. at Stanford University and has been widely used by the Puerto Rico Department of Health since it is recommended by the CDC as an evidenced-based intervention for chronic disease management.

[figure not shown]

Figure 2: Summary of study recruitment and procedures, PR COAS\_TCS

The intervention consists of small group workshops with 8 to 15 participants lead by two certified trainers, offered virtually or face-to-face (at the EHSRC Office of Clinical and Community Health Research located at the Hospital UPR in Carolina) for 2 1/2 hours once per week for six-week period open to Spanish-speakers with any physical or mental chronic condition or multiple chronic conditions. As part of the intervention, a pre and post TCS assessment will be collected.

Topics included in the training are:

- 1) Healthy eating
- 2) Appropriate exercise for maintaining and improving strength, flexibility, and endurance
- 3) Managing depression
- 4) Appropriate use of medications

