The last interview of the cohort study (PR-COAS) in which the participants will be identified, which collect information on general aspects of self-care of chronic diseases, healthcare utilization, vaccination status, lifestyles modifications, and health-related quality of life among others, will be used as baseline for the purposes of this study. In addition, a follow up interview will be coordinated one month after completing TCS for the intervention group and approximately 3 months after the last interview of the cohort study for the control group. The following indicators will be collected: Health care services utilization (primary care, emergency room and hospitalizations), compliance with prescribed medications, risk behaviors (such as smoking, physical activity, alcohol use), nutritional awareness, self-efficacy for disease management based on the level of confidence) and quality of life. The standard data collected by the PRDOH for this intervention (*Formulario 1: Formulario Inicial, Preprueba, and Formulario 2: Formulario Final, Post-Prueba & Evaluación, Rev. Enero 2022*) will also be used for analysis. The Form 1 is a self-administered questionnaire of 28 closed-ended questions that collects TCS participants' sociodemographic and contact information (name, municipality of residence, marital status, education, age, sex, medical plan, email), general information on diagnosed health chronic conditions, COVID-19 vaccination, level of confidence in managing chronic conditions, general health, use of health services, and lifestyles (e.g. consumption of vegetables, fruits and alcoholic beverages, physical activity and whether or not you smoke). The Form 2 is a 40-question self-administered questionnaire that mainly collects general information about the lifestyles of TCS workshop participants (consumption of vegetables, fruits and alcoholic beverages, physical activity and whether or not they smoke), general health status, level of confidence in managing health chronic conditions, utilization of health services, attendance, evaluation and experience in TCS workshop.

The impact of health-related quality of life will be assessed using the following scales:

- EQ-5D-5L (Spanish version), which includes five dimensions: mobility, self-care, daily activities, pain or discomfort, and anxiety or depression.
- Fatigue (NIH PROMIS® Neuro-QoL Item Bank v1.0, Short Form, Spanish version)

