## HUMAN SUBJECT PROTECTION

**Consent process:** After the patient expresses interest in participating in the study, study staff will contact the potential participant via phone or face to face to discuss the study informative sheet following the appropriate consent process as described in the method section. The consent process will be done only by the investigators, study staff, or trained interviewers. The study coordinator will oversee the training of the interviewers about the process of consent by the discussion of the informative sheet and the study procedures prior to any contact with potential participants. A script will be developed to explain the process of consent over the phone. The information in the script will include the purpose of the study, duration of subject participation, description of the procedures, risks, benefits, and confidentiality. In addition, it will include information about the voluntary nature of participation and whom to contact for questions. During the process, the subjects will have the opportunity to ask questions, and if the potential participant requests any other information about the study, it will be provided. Although a written consent form will not be collected, the person who will conduct the discussion of the informative sheet should document all the activities, including the date and time of the call, duration, and if there were questions regarding the process. The person in charge of the consent process should also document and certify in a form that the information provided by them is correct and that the subject consented.

Participants will receive an incentive for transportation and/or parking expenses and for the time dedicated for their participation. The intervention group will receive \$25 for each session of the TCS workshop. This incentive will be given to them at the end of each session at the Endowed Health Services Research Center (EHSRC). Upon completion of the final interview, one month after the end of the workshop, the participant will receive a \$25 incentive that can be sent to them by certified mail or can be hand-delivered at the EHSRC office in a specific time scheduled. In the

case of the non-intervention group, participants will receive a \$25 incentive upon completion of the final interview, approximately 3 months after completing the baseline interview, that is, the final PR-COAS interview.

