**TABLE 2: PROPOSED TIMELINE**

		9 - Months								
Proposed Activities		1	2	3	4	5	6	7	8	9
Intervention for Long-COVID – chronic disease self-management	Training or recruitment of trainers for “Tomando Control de su Salud” intervention	X	X							
	Submission and approval of IRB		X	X						
	Participant selection and group allocation				X	X	X			
	Intervention workshops (8 – 12 participants)							X	X	
	3-month follow-up interview								X	X
	Data analysis and dissemination							X	X	X

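### Follow-up is tied to baseline in the control arm but to the workshop in the TCS arm, so the difference in change can include unequal elapsed time

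*Combined protocol and SAP*

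**What the plan says.** **Baseline.** Methods, Participant selection: "We will invite patients from our cohort study during the 12-month follow-up call". Methods, Outcome measures: that last cohort interview "will be used as baseline for the purposes of this study". Invitation and baseline therefore coincide, and both arms share them.

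**Follow-up.** Outcome measures states: "a follow up interview will be coordinated one month after completing TCS for the intervention group and approximately 3 months after the last interview". The second timing is the one for controls and runs from the shared baseline. Sampling strategy repeats the control timing. The Consent process section repeats it too, but describes the TCS interview slightly differently: "Upon completion of the final interview, one month after the end of the workshop".

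**Calendar.** The programme runs "once per week for six-week period" (Proposed intervention). Table 2 puts "Participant selection and group allocation" in months 4 to 6 and workshops in months 7 to 8. It has one follow-up row, labelled as a three-month interview and not split by arm, in months 8 to 9. Specific Aim 2 (behaviour level) gives yet another timing, 3 to 6 months after the programme is implemented.

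**Analysis.** Data analysis estimates the change in each group and the difference in change between groups, with confidence intervals and rank tests on the change scores. It has no term for time since baseline. No section limits the time from baseline to the first session.

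**The concern.** Arms are formed by interest in the workshops, not by randomisation. The main thing the control group can then offer is to subtract change that would have happened anyway, and it does so cleanly only if both arms had the same time in which to change. Here the control interval is fixed from baseline, while the TCS interval depends on the wait for a workshop.

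The pilot's stated product is an effect size for planning a larger study, so a shift caused by scheduling would carry into that plan. Later adjustment is a weak remedy. Controls would cluster near 3 months and most TCS participants would lie beyond it, so elapsed time would be largely confounded with arm.

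The TCS trigger is also worded in two ways, completion of the programme and end of the workshop, and no rule covers people who stop attending.

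**Working it through.** No sample-size formula applies, so the check is calendar arithmetic. One month is taken as 52.18/12 = 4.35 weeks.

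**1. The plan's own figure.** Controls: 3 months = 13.04 weeks from baseline.

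**2. TCS interval.** Wait W + 6 weeks of sessions + 1 month = W + 10.35 weeks, or W + 2.38 months.

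| Wait W (weeks) | TCS interval (months) |
|---|---|
| 0 | 2.4 |
| 2.7 | 3.0 |
| 4 | 3.3 |
| 8 | 4.2 |
| 13 | 5.4 |
| 15.7 | 6.0 |

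The arms match when W = 13.04 − 10.35 = 2.7 weeks (3.7 weeks if six weekly sessions are counted as 5 weeks from first to last). The protocol requires neither.

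**3. Table 2, TCS arm.** Let month n run from n−1 to n. Assumptions: baseline b is spread evenly over 3 to 6 (mean 4.5), and each six-week workshop fits inside months 7 to 8. Then:

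- The start s lies between 6.0 and 8 − 1.38 = 6.62.
- The interview falls at s + 2.38, that is 8.38 to 9.0.
- Shortest interval: 8.38 − 6 = 2.4 months. Longest: 9.0 − 3 = 6.0 months.
- Mean interval: 8.38 − 4.5 = 3.9 months if all workshops start at the beginning of month 7; 9.0 − 4.5 = 4.5 months if all start as late as possible.
- With starts spread evenly between those limits, the mean is 4.2 months, about 90% of TCS participants exceed 3 months, and about 25% fall within two weeks of it.

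**4. Table 2, control arm.** If the text is followed, 3.0 months. If no interview takes place before month 8 (time 7), controls with b between 3 and 4 wait 7 − b, mean 3.5 months. The control mean is then (1/3)(3.5) + (2/3)(3.0) = 3.17 months.

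**5. Mean gap.** Smallest: 3.88 − 3.17 = 0.7 months. Largest: 4.50 − 3.00 = 1.5 months.

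**6. Bias from drift.** Bias = r × gap, with r the change per month without any programme effect, in SDs of the change score. The documents give no r, so the values are assumed.

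| r (SD/month) | Bias at gap 0.7 to 1.5 months (SD) |
|---|---|
| 0 | 0 |
| 0.02 | 0.01 to 0.03 |
| 0.05 | 0.04 to 0.075 |
| 0.10 | 0.07 to 0.15 |

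**7. Precision for comparison.** The 95% half-width is 1.96 × √(1/n₁ + 1/n₀) SD, with the expected sizes in Sampling strategy. For 20 versus 30: 1.96 × 0.289 = 0.57 SD. For 25 versus 40: 1.96 × 0.255 = 0.50 SD.

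**The case against.** **The strongest case.** This is an unpowered, non-randomised pilot with self-selected arms, and any drift bias is small beside the sampling error. Participants are already at their 12-month cohort interview, and the Background expects symptoms to last a long time, so drift may be slow or nil. Table 2 is only a proposed timeline, and its single follow-up row suggests that comparable timing was intended.

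Most of this stands, and it limits the severity. The bias is conditional on drift, and zero is within the plausible range. But sampling error is random, whereas a scheduling gap acts in the same direction for most TCS participants and does not shrink with more of them. The intention behind Table 2 is not secured by the text, which fixes one arm's interval and leaves the other open.

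**Stronger readings that the documents do not support:**

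- *TCS participants are followed for one month and controls for three.* The two figures have different origins. Six weeks plus one month is already 2.4 months from baseline, and Table 2 implies a mostly longer TCS interval.
- *The TCS arm becomes completers only.* Outcome measures does speak of completing TCS, but the Consent process section dates the interview from the end of the workshop, and no section excludes partial attenders. The wording is ambiguous. The documents give no drop-out rate or outcome deficit from which to size an effect.
- *Service-use counts cover different windows.* No recall period is stated. Items with a fixed recall period would cover equal windows, so this is a risk, not a finding.
- *The bias reaches 0.30 SD.* That is 3.0 months × 0.10 SD. It applies only to the earliest recruits in the latest workshop under the fastest assumed drift, and is not a difference between arm means.

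**Conclusion.** The point holds as a should-fix. As written, the plan does not give the two arms the same time from baseline, and the analysis does not account for the difference. The estimated gap rests on three assumptions: baselines fall evenly in the selection months, workshops fit inside months 7 to 8, and the participants follow Table 2. The existence of two clocks rests on the text alone. The size of any resulting bias depends on a drift rate that the documents do not give. On the assumed range it is modest and could be zero, but it would pass unseen into the effect size that the pilot is meant to deliver. Aligning the clocks would leave confounding by interest in the intervention untouched.

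**What to change.** 1. State one target interval from baseline, with a window, for both arms. Schedule control interviews so that their elapsed times have the same distribution as those in the TCS arm. Match on baseline date, because a workshop may mix recruitment months.
2. Anchor the TCS interview at one month after the workshop's scheduled end date for everyone who accepted TCS, whatever their attendance. Make Outcome measures and the Consent process section agree on this.
3. Record days from baseline to follow-up, report them by arm, and adjust for them in a sensitivity analysis.
4. Use one fixed recall window for health-care utilization in both arms.
5. Reconcile the follow-up timings in Specific Aim 2, Sampling strategy, Outcome measures, the Consent process section and Table 2.

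**Cost.** Amended wording and re-timed control interviews, with none added. Relative to 3 months, control calls would move from about half a month earlier (2.4 − 3.0 = −0.6) to 3 months later (6.0 − 3.0), mostly later. Under the Table 2 assumptions, matched interviews would fall at 8.38 to 9.0, within the existing follow-up row, but they would concentrate interviewer workload in month 9.

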**Table 1: Data to be collected at baseline and follow up interviews**

Indicator	Variables	Source of questions
General health and lifestyles	Health perception and disability Lifestyles and risk behaviors: consumption of vegetables, fruits, tobacco use, alcohol consumption, and physical activity	RADx-UP  , PROMIS-10 Global Health, v1.2  , All of Us Surveys  and WHO Global COVID19 Clinical Platform  , Cuestionario del BRFSS 2020 
Vaccination	Vaccination status and perceptions	CEAL Common Survey 2  , RADx-UP  , All of Us COPE Survey COVID-19  and Folcarelli et al. , 2021 
	Compliance with booster recommendations	CEAL Common Survey 2  , Folcarelli et al. , 2021  , and new questions
	Access and perceived barriers	CEAL Common Survey 2  , Folcarelli et al. , 2021  , Yoshida et al. , 2022  and new questions
Management of health chronic conditions	Health chronic conditions, use of medications, medical consultations, self-care, disease monitoring, self-management	BRFSS 2020  , PhenXToolkit  , Self-Care of Chronic Illness Inventory (SC-CII v4.c, Spanish version) 
Self-Efficacy for Managing Chronic Conditions	Daily activities, medications and treatment, symptoms, social interactions, emotions	PROMIS Item Bank v1.0 - Self-Efficacy for Managing Chronic Conditions - Short Forms 4a 
Healthcare utilization for chronic diseases	Health care access, postponed medical procedures, studies and appointments, missed scheduled appointments with any health care provider, missed taking any medications, healthcare challenges	PhenXToolkit  , CDC National Health Interview Survey (NHIS) Utilization Questionnaire, 2020  , BRFSS 2020  , Ryder et al. 2022  , Singh et al. , 2021  , Uzun, et al. , 2023  , Abraham et al. , 2023  , new question
Quality of life assessment (follow up)	Health-related QoL (HRQoL) scales: 
 
EQ-5D-5L
 
PROMIS v1.0 Fatigue SF for adults
 
The Post-COVID-19 Functional Status (PCFS)
 
Anxiety (GAD-7)
 
	PROMIS Health Measures  , EQ-5D-5L  , PCFS  , GAD-7 

**Data management:** Trained interviewers will collect data through structured interviews. To ensure the quality of the data collection process, all interviewers will receive an intensive training session regarding the consent process, interviews, and data collection process. This training will include using the questionnaires and standardized electronic forms for the data collection, along with a protocol that clearly outlines how the information will be collected. Although a unique study identification number will be assigned to each patient, we will maintain patient identifiers to be able to contact them in the follow-up interviews. These identifiers will include name, physical address, postal address, phone, email, and Facebook contact. After finishing the data collection process and following up with the patients and database cleaning, all personal identifiers will be removed, and the final database for analysis will be anonymized.

Participant-specific data will be entered via a web-based interface using Research Electronic Data Capture (REDCap) (Harris et al., 2009). REDCap is a secure, web-based application that allows the construction and implementation of online instruments. We will program the system with validation rules at the time of entry, and comprehensive edits after data has been submitted to the main database. Edits will check for validity, consistency, and normal range values. As part of our standard operating practices, we will implement a data cleaning protocol, which checks for consistency and examinations of frequency tabulations.

This project will strictly apply all procedures established by the UPR-School of Medicine for data security and management. The collected information and any other relevant document will be kept strictly confidential. To ensure confidentiality, all study data and documents will be kept secured with locked files in the clinic area of the Office of Clinical and Community Health Research of the EHSRC located on the Ground floor of the UPR Hospital in Carolina, PR. Electronic data will be password-protected and not be shared through emails or clouds. To protect the study data from improper use and disclosure, we will assign a study number to each questionnaire and de-

identify the databases. Study data and related documents will be kept for five years and then destroyed.

**Data analysis:** Since this is a pilot study the primary focus of the statistical analysis of this study is estimation (effect sizes and associated uncertainty). We will conduct pre- and post-intervention analysis among participants of the intervention group and between group comparisons with intervention and non- intervention groups. Descriptive analyses will be done using frequency distribution and contingency tables for categorical data. Continuous variables will be reported using mean, median, standard deviation, inter-quartile range and range. Chi-square or Fisher's exact test will be done to assess differences in sociodemographic or health indicators between the groups and to compare the independent domains of the quality-of-life scale among patients in the intervention or non-intervention group. To evaluate changes in quality of life before and after the intervention, estimates and 95% confidence intervals will be generated based on the change scores, i.e., using paired data with each subject acting as their own control. Estimates and confidence intervals will be provided for both the individual group changes as well as the difference in change between each pair of groups. We will perform Wilcoxon/Mann-Whitney U-tests (non-parametric) comparing the change scores in each group with each other. These Wilcoxon tests will be performed in addition to a Kruskal-Wallis test (non-parametric ANOVA) in order to test for an overall group effect. The Wilcoxon paired sample test will be used for ordinal data and the Mc Nemar test for significant changes will be used to evaluate dichotomous data. All analyses will be conducted using Stata version 11(Stata Corporation, College Station, Texas, USA).

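### Chi-square or Fisher tests on the EQ-5D-5L dimensions use neither level order nor baseline and give no effect size; the follow-up comparison needs an ordinal, baseline-adjusted estimate

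*Combined protocol and SAP*

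**What the plan says.** The outcome list in METHODS names the EQ-5D-5L, "which includes five dimensions: mobility, self-care, daily activities, pain or discomfort, and anxiety or depression". The Data analysis section of METHODS then does three things.

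- It assigns chi-square or Fisher's exact test to group differences in sociodemographic or health indicators and "to compare the independent domains of the quality-of-life scale among patients in the intervention or non-intervention group". No time point is given, and nothing says whether the levels are kept or collapsed.
- It plans change analyses for quality of life. The estimation part reads: "Estimates and confidence intervals will be provided for both the individual group changes as well as the difference in change between each pair of groups". Rank tests of those changes between groups (Mann-Whitney for pairs of groups, Kruskal-Wallis overall) are added. Nothing says whether these cover each dimension or only scale scores.
- For paired data it recognises ordinal outcomes: "The Wilcoxon paired sample test will be used for ordinal data".

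It also states that "the primary focus of the statistical analysis of this study is estimation (effect sizes and associated uncertainty". The sample size paragraph adds: "We are therefore not powering for a definitive assessment of the difference between any two groups".

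**The concern.** An EQ-5D-5L dimension is an ordered item (five levels, read from the instrument's name; the documents do not describe them). Chi-square and Fisher tests treat the levels as unordered categories, or require them to be collapsed, and they make no use of the person's baseline level.

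Three things are at stake if the sentence means a follow-up comparison:

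- **Bias.** The trial is non-randomised, and the general care group consists of people who did not want the workshops. A follow-up-only comparison mixes where people started with what the workshops did.
- **Estimation.** A chi-square or Fisher p-value supplies no effect size or interval, which is what this pilot is meant to deliver for planning a larger study.
- **Sensitivity.** With two small arms and five levels the tables are sparse, so the test can miss a shift that an ordered analysis would show.

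**Working it through.** The documents give no power, alpha or effect size, so there is no planned figure to reproduce.

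**Inputs from the documents**
- Arms: 20–25 intervention and 30–40 general care (Sampling strategy); 22 and 35 used.
- 52% of Long COVID patients had pain or discomfort (Background), so 48% are placed at the best level.

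**Assumed inputs**
- The other levels at 25, 15, 8 and 4%.
- A latent normal scale with baseline to follow-up correlation ρ = 0.6.
- Shifts of 0.5 and 0.8 SD; two-sided 5% level.

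**Step 1: sparseness.** Expected counts at the two worst levels are 22 × 0.08 = 1.8 and 22 × 0.04 = 0.9 in the intervention arm, and 35 × 0.08 = 2.8 and 35 × 0.04 = 1.4 in general care.

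**Step 2: simulated power with no baseline imbalance**

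| Analysis | 0.5 SD | 0.8 SD |
|---|---|---|
| Chi-square, 2×5, follow-up | 12% | 30% |
| Fisher, none vs any problem, follow-up | 24% | 55% |
| Mann-Whitney, follow-up levels | 32% | 65% |
| Mann-Whitney, change scores (planned) | 28% | 50% |
| Rank ANCOVA on baseline | 41% | 77% |

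As a share of rank ANCOVA power:
- chi-square keeps 12/41 = 0.29 and 30/77 = 0.39;
- dichotomised Fisher keeps 24/41 = 0.59 and 55/77 = 0.71;
- the change test keeps 28/41 = 0.68 and 50/77 = 0.65.

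A repeat run of 2,500 trials per setting agreed to within about two percentage points. With no effect, chi-square rejected 3.7% and the baseline-adjusted rank analysis 5.7%, so the gap is not explained by a badly inflated error rate.

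**Step 3: sensitivity.** The grid covered 52, 37 and 24% with any problem, arms of 20 vs 30 and 25 vs 40, and ρ from 0.3 to 0.85, at shifts of 0.5 to 0.8 SD. Relative to rank ANCOVA:
- Chi-square 2×5 keeps 0.11–0.52 of the power (median 0.26) and is below half in 98% of settings.
- Dichotomised Fisher keeps 0.45–0.88 (median 0.72) and is below half in 10%.
- Fisher's exact test on all five levels keeps 0.14–0.54 at ρ 0.5–0.7, and 0.50–0.79 at a shift of 1.2 SD. That grid was only partly run.

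**Step 4: how much is order and how much is baseline.** Without baseline the SD is 1; after adjustment it is √(1 − ρ²). For 30 vs 20 and a 0.5 SD shift, power is 41% from follow-up only, and 44, 52, 68 and 91% adjusted at ρ = 0.3, 0.5, 0.7 and 0.85. Ignoring baseline alone costs more than half only near ρ = 0.85 (41/91 = 0.45). In a five-level chi-square, ignoring order does most of the damage: it has 0.17–0.54 (median 0.34) of the power of Mann-Whitney on the same follow-up values.

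**Step 5: self-selection.** Suppose there is no effect and the workshop arm is stably 0.5 SD better at both times. The gap left is 0.5 SD at follow-up, 0.5 × (1 − 0.6) = 0.2 SD after baseline adjustment, and 0 in the change. Simulated false rejections: Fisher 25%, chi-square 13%, rank ANCOVA 15%, change test 4%.

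If instead there is a true 0.5 SD benefit and the arm starts 0.5 SD worse, chi-square rejects 4%, Fisher 3%, rank ANCOVA 15% and the change test 41%.

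**The case against.** The strongest reply is that the plan already contains between-arm analyses that use order and baseline: the difference in change with its interval, and the Mann-Whitney tests on change scores. A reader might infer from the chi-square sentence that the trial throws away more than half its power. The documents do not support that. The planned change test keeps about two thirds of rank ANCOVA power in the table above. What remains is that the section does not say the change analyses apply to each dimension, while chi-square/Fisher is the only between-group method explicitly attached to the domains.

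The sentence also follows the descriptive methods and may mean a baseline or descriptive comparison, in which case the power and carry-over arguments fall away. The Background reports domain results as two-group percentages (24% vs 9%, 52% vs 17%, 37% vs 11%), which suggests dichotomising, where the loss is smaller. Both readings are open, and the text should settle them.

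Power is not this pilot's criterion. That is correct, but it strengthens the call for an estimate with an interval in place of a p-value.

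A reader might also extend the criticism to the Post-COVID-19 Functional Status Scale. The sentence concerns only domains of the quality-of-life scale; no section assigns chi-square to that instrument.

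**Conclusion.** The concern holds conditionally. If chi-square/Fisher is applied to follow-up EQ-5D-5L levels, it discards order and baseline, yields no effect size, and lets baseline differences between self-selected arms pass as effect or hide one. With five levels kept and shifts of 0.5 to 0.8 SD, chi-square power is about 12–30% against 41–77% for a baseline-adjusted rank analysis. With dichotomised dimensions Fisher has about 24–55%, and the relative loss shrinks for large effects.

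These figures rest on an assumed effect, correlation and level distribution. They treat one dimension at a time, without multiplicity or workshop clustering. They were obtained with rank ANCOVA; the proportional-odds model was not itself simulated. They describe one named test, not the power of the plan as a whole. Bias and the missing effect estimate are firmer grounds than power. This is a worthwhile and inexpensive improvement, not a flaw that undermines the pilot.

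**What to change.** In the Data analysis section:

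1. State the time point and coding of the domain comparison.
2. For the between-arm comparison of each EQ-5D-5L dimension at follow-up, replace chi-square/Fisher with a proportional-odds model of follow-up level on arm, with baseline level as covariate, reporting the common odds ratio and 95% CI. Where levels are too sparse, use rank ANCOVA, which keeps the baseline adjustment.
3. State that the planned difference in change, with its interval, is also applied to each dimension, and report the two side by side. Step 5 shows that they can diverge when the arms start apart.
4. Keep chi-square/Fisher for baseline characteristics and for descriptive percentages with any problem.

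Cost: a few sentences and standard commands. Baseline comes from the last cohort interview, which the plan already uses for this purpose. The downside is a proportional-odds assumption that a sample of this size can barely check. Adjusting for one baseline item reduces self-selection bias but does not remove it, and the report should say so.
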